Protocol March 7, 2018

Androgen Excess as a Cause for Adipogenic Dysfunction in PCOS Women

NIH Prime Award No 1U54HDO71836-01A1, Subaward #9009028 UCLA

NCT01889199

UCLA IRB #12-001780

Principal Investigator

[name] Chief, Division of Reproductive Endocrinology and Infertility UCLA Department of Obstetrics and Gynecology

Co-Principal Investigator

[name] Division of Reproductive Endocrinology and Infertility UCLA Department of Obstetrics and Gynecology

Co-Investigators

[name] UCLA Department of Plastic Surgery

[name] UCLA Department of Radiological Sciences

[name] [name] UCLA Department of Radiological Sciences

Collaborating Investigator

[name] Department of Obstetrics and Gynecology University of Wisconsin, Madison Revised 3-7-18 UCLA IRB #12-001780 Page 2 of 27

LAY SUMMARY

The purpose of this research study is to collect specimen samples and study medical information from women with Polycystic Ovary Syndrome (PCOS) and women without PCOS. The goal is to learn more about the changes that take place in the body that result in PCOS.

We anticipate that 70 women will be enrolled in this study (20 without PCOS and 50 with PCOS). All patients will undergo a physical exam, blood tests, and transvaginal ultrasound of their ovaries. If they meet the criteria for this study, they will then undergo additional blood tests, removal of abdominal fat, transvaginal ovarian ultrasound, MRI, DXA scan, frequently-sampled intravenous glucose tolerance test (FSIGT), follicle stimulating hormone stimulation test, and Quality of Life surveys. The women without PCOS will be complete the study at this point.

The women with PCOS will be stratified according to whether they are insulin resistant or non insulin resistant based upon the results of their glucose tolerance test. Both groups will be randomized to receive the drug flutamide 125 mg/day or placebo. Subjects will take the drug/placebo every day for 6 - 28 day cycles and will continue to take the drug/placebo until all post treatment assessments are completed. Subjects will be asked to collect and store a urine sample once a week during the 6 - 28 day cycles. Subjects will also be asked to complete diaries. Once a month while they are taking the flutamide/placebo, they will return to the clinic and bring their urine samples. At that time they will undergo a physical exam, toxicity assessment, and blood draw. Quality of Life surveys will be performed at baseline, midpoint, and end of study for PCOS participants. Non-PCOS participants will complete Quality of Life surveys at baseline only.

After the 6 - 28 day cycles are completed the PCOS participants will continue to take study drug/placebo until they have completed end of treatment evaluations which include physical exam, additional blood tests, removal of abdominal fat, trasvaginal ovarian ultrasound, MRI, DXA scan, frequently-sampled intravenous glucose tolerance test (FSIGT), and follicle stimulating hormone stimulation test.

Per amendment #11 submitted 11-25-13, subjects who previously underwent an OGTT will be asked to undergo an FSIGT. Women enrolled on the PCOS arm may choose to decline the FSIGT and will undergo an OGTT post treatment.

Per Amendment #24 submitted 6/10/15, we requested permission to add a Family History Questionnaire to this study. Subjects who have been enrolled in the past as well as future participants will be asked to complete the questionnaire. Active study participants will be asked to complete the questionnaire at their next regularly scheduled study visit. Those who have completed all of their study visits will be contacted by phone or email to ask if they will complete the questionnaire. If they agree, it will be sent to the participant by US mail with a stamped return envelope or the questionnaire will be completed over the phone. New study participants will be asked to complete the questionnaire at their eligibility visit. If any participant(s) decline, their participation in Revised 3-7-18 UCLA IRB #12-001780 Page 3 of 27

this study will not be affected nor will their future healthcare at UCLA.

BACKGROUND AND SIGNIFICANCE

Polycystic ovary syndrome (PCOS): PCOS, a common endocrinopathy affecting 6–10% of women, manifests by hyperandrogenism, ovulatory dysfunction and polycystic ovaries (PCO) in its complete phenotype. Abdominal adiposity occurs frequently in PCOS women vs. controls, including some, but not all, nonobese individuals. Consequently, the estimated prevalence of MBS in PCOS is 33-47%, about 2-3 times higher than that of age-matched controls.

Interplay between adipose function and androgen excess: In PCOS, intrinsic defects combine with endocrine factors to impair insulin sensitivity and induce adipocyte insulin resistance (IR). Conversely, physiological androgen administration to women induces IR. In PCOS women, therefore, androgen excess could decrease numbers of SC abdominal adipocytes and reduce capacity of this adipose to safely store fat. Thus, if energy intake exceeds this capacity, SC abdominal adipocytes would likely overfill with lipid to promote ectopic lipid deposition. We hypothesize that PCOS-related hyperandrogenism decreases adipogenic differentiation and increases adipocyte lipid content in a constrained SC abdominal adipose, inducing lipotoxicity, IR and ovulatory dysfunction.

Therefore, reducing PCOS-related androgen excess could improve SC abdominal adipogenic function and ovarian folliculogenesis, reducing use of ovulation-inducing agents in PCOS women wishing to conceive, and risks of multiple pregnancy.

Effect of flutamide on PCOS: Administration of flutamide, a nonsteroidal anti-androgen, to PCOS women lowers circulating androgen and triglycerides levels. Flutamide also restores ovulation in some, but not all, PCOS women. We will systematically compare SC abdominal adipogenesis, circulating adipogenic markers and SC abdominal as well as visceral (omental plus mesenteric) adipose content of lean PCOS women randomized to 6-month low-dose flutamide vs. placebo to determine how differences in key variables affect ovarian function and morphology, as well as in vivo E2 responsiveness to FSH.

We also are able to quantify SC abdominal and visceral adipose content by magnetic resonance imaging (MRI), as performed by [name]. Finally low-dose flutamide vs, placebo administration to lean PCOS women will discover novel molecular and biochemical markers that predict efficacy of androgen blockade in restoring adipogenic and ovarian function.

AIMS AND OBJECTIVES

The purpose of this research study is to collect specimen samples and study medical information from women with PCOS and women without PCOS. The goal is to learn more about the changes that take place in the body that result in PCOS.

Revised 3-7-18 UCLA IRB #12-001780 Page 4 of 27

Our Aims are to:

Aim 1: Compare differences in SC abdominal adipose structure-function and regional abdominal adipose content in lean PCOS women vs. age- and BMI-matched controls. Hypothesis: SC abdominal adipose storage is constrained in lean PCOS women.

• Analyze adipocyte size, lipid accumulation, function and secretion of adipokines.

• Analyze same parameters indicated above and signaling pathways in new adipocytes originated from isolated adipose stem cells.

• Use cell culture to examine interactions between adipose stromal-vascular cells and adipocytes in the control of adipose development.

• Correlate key factors with insulin action in vivo; regional and percent body fat; circulating lipids, free fatty acids (FFAs), sex steroids, and adipokines; and ovarian volume, antral follicle number and serum AMH as well as serum E2 response to recombinant human (rh)FSH per antral follicle.

Aim 2. Examine effect of flutamide on SC abdominal adipose structure-function, regional abdominal adipose content and ovarian folliculogenesis in lean PCOS women. Hypothesis: SC abdominal adipose storage is normalized in lean PCOS women receiving flutamide.

• Examine in vitro effects of sex steroids on adipogenesis.

• Determine changes in SC abdominal adipogenesis, circulating lipids, FFAs, sex steroids, and adipokines.

• Determine changes in SC abdominal and visceral adipose content, fat free mass as well as percent body fat.

• Determine changes in ovarian morphology and function as well as ovulatory frequency, as measured by weekly urinary pregnanediol glucuronide (UPDG).

• Determine key factors that predict ovulation by serial urinary UPDG measurements.

RESEARCH DESIGN AND METHODS

Aim 1. Compare differences in SC abdominal adipogenesis of lean PCOS women vs. age- and BMI-matched controls

Subjects and clinical assessment: We will recruit subjects with the intention of enrolling 90 women - 70 lean (18.5-25 kg/M2) PCOS subjects and 20 age- and BMI-matched controls with the assumption that there will be dropouts such that 36 women with PCOS and 12 controls will complete the study. Subjects will complete a standardized questionnaire emphasizing menstrual dating, abnormal hair growth and acne. The questionnaire also will annotate age, smoking status, medications, surgical history and family histories of excess hair growth in female relatives and of diabetes in parents or siblings for exclusion criteria and for inclusion of some basic traits as covariates. Subjects also will undergo a physical examination; hirsutism will be scored by the modified Ferriman-Gallwey (mFG) method. Transvaginal sonography (TVUS) will be performed to determine the presence or absence of polycystic ovaries by Rotterdam

Revised 3-7-18 UCLA IRB #12-001780 Page 5 of 27

criterion. A screening blood sample will be obtained for determinations of steroid hormones, TSH, and prolactin; biochemical hyperandrogenism will be defined as an elevated serum total or free T > 2 SD above the mean value. Non-Hispanic Caucasian women between the ages of 18 and 35 years will be recruited to avoid confounding differences as a function of race. PCOS patients will be diagnosed by 1990 NIH criteria. Controls will have regular menstrual cycles at 21 to 35 day intervals, a luteal phase progesterone (P4) level > 3 ng/mL, and no evidence of hirsutism, acne, alopecia, polycystic ovaries or endocrine dysfunction. Exclusion criteria are: present/past history of smoking during the past year, cancer, alcohol abuse, drug addiction, severe depression, or post traumatic stress; diabetes; uncontrolled hypertension (\geq 165/100); clinically significant hepatic or renal disease, or other major medical illness; signs or symptoms of infection; recent (within 30 days) use of an experimental device; recent (within 6 months) use of androgens, anabolic steroids or non-steroidal anti-inflammatory drugs; recent (within 3 months) use of hormonal agents (including birth control pills, Plan B, Mirena IUD, or insulin sensitizers); use of the drug warfarin; beta blockers; CYP active medications or herbs.

Frequently sampled intravenous glucose tolerance test (FSIGT): All studies will be conducted in the follicular phase in controls and during amenorrhea in PCOS women. Each subject will be instructed to drink only water during the 12-hour fasting period before the FSIGT, and to avoid caffeinated fluid intake. Glucose in the form of a 50% solution (0.3 g/kg) and regular human insulin (0.03 units/kg) will be injected through an intravenous line at 0 and 20 min, respectively. Blood will be collected at -20, -15, -5, 0, 2, 4, 8, 19, 22, 30, 40, 50, 70, 90, and 180 min for glucose and insulin determinations. Approximately 2-3 tablespoons (28-42 ml) will be drawn for the FSIGT test. Adipocytes isolation and culture: Approximately 1.0 gm of fat will be obtained from the lower SC abdomen using standard procedures under local anesthesia. Adipocytes and the stromal vascular fraction will be isolated to measure adipocyte cell number and diameter, lipid accumulation and function, adiponectin, and stem cell development.

Procedures: All procedures will be performed in normal and PCOS women at the start of study.

i). Venipuncture: Fasting blood will be collected for blood count, chemistry panel, LH, FSH, total/free T, DHT, A4, DHEAS, E1, E2, anti-mullerian hormone (AMH), SHBG, adiponectin, IL-6,lipid profile, C-reactive protein, glucagon, leptin, C-peptide, and FFAs. Blood samples for all participants will be shipped to Oregon State Health University (OHSU) for analysis of AMH, IL-6, adiponectin, glucagon, leptin, and C-peptide levels. The University of Michigan will perform a comprehensive hormone analysis by LC-MS/MS, including traditional (T, AD, DHEA, DHEAS) and emerging androgen biomarkers (11-oxygenated C19 steroids, 11 OHA, 11KA, 11OHT, 11KT). There will be no personal identifiers on the samples that sent to OHSU or University of Michigan.

Study numbers will be used.

ii). Body composition: Body composition will be assessed by BMI, waist-to-hip circumference and DXA scanning. Girths will be measured at the waist (narrowest section of the torso between ribs and umbilicus) and hips (largest protrusion of the hip region, above the gluteal fold). For total body fat and regional fat distribution (central vs. appendicular), whole body scans will be performed, utilizing DXA imaging (Hologics QDR 1500). A portable BIA will calculate lean body mass changes by computerized methods to measure resistance and reactance.

iii). Body fat distribution: Total body DXA will measure abdominal fat (i.e., the area between the dome of the diaphragm [cephalad limit] and the top of the greater trochanter [caudal limit]). Total body DEXA images also will determine % body fat; fatfree body mass; total body, abdominal, and leg fat; and abdomen/leg fat mass ratio. The leg region is that area below the top of the greater trochanter. Multiple axial abdominal and pelvic MRI slices from the diaphragm to the pelvis will assess cross-sectional areas of SC abdominal and visceral fat.

iv). Ovarian testing:

a). Ovarian morphology: TVUS using a 4- to 8-mHz vaginal probe will be performed in the follicular phase in controls and during amenorrhea in PCOS women. Summed ovarian volume will be calculated. Antral follicle number, defined as the total follicle number (2-9 mm in diameter) of both ovaries, will be determined by 1 investigator ([name]). Polycystic ovaries will be defined by 12 or more follicles in each ovary measuring 2-9 mm in diameter, and/or increased ovarian volume (> 10 ml), with one such ovary sufficient to define PCO.

b). E2 response to recombinant human (rh)FSH. Blood samples will be drawn through an indwelling iv catheter at -90, -60, -30 minutes and time 0 as well as 0.5, 1, 1.5, 2, 3, 4, 6, 8, 10, 12, 16, 20, and 24 h after 150 U rhFSH injection (112). The E2 response to rhFSH will be assessed before and after adjusting for numbers of TVUS-detected ovarian antral follicles.

Aim 2. Examine effect of flutamide in lean PCOS women on SC abdominal adipogenesis, visceral adipose content and ovarian folliculogenesis.

Per amendment #29, we are requesting permission to change the randomization strategy since all PCOS subjects enrolled thus far have been non-insulin resistant

Revised 3-7-18 UCLA IRB #12-001780 Page 7 of 27

based upon the results of the Frequently Sampled Intravenous Glucose Tolerance Test. Therefore, the need to stratify the PCOS subjects into two groups (i.e. insulin resistant versus non-insulin resistant) is unnecessary. All PCOS subjects recruited will now be randomized to study drug versus placebo based upon non-insulin resistant status. Of note, the control subjects are not randomized since they do not receive study drug or placebo.

Adipogenic studies: All adipogenic studies performed at study initiation will be repeated at the end of the 6 - 28 day cycles of flutamide vs. placebo intervention in PCOS women.

Procedures: All procedures performed at study initiation also will be repeated at the end of the 6 - 28 day cycles of flutamide vs. placebo intervention in PCOS women. The end of treatment fat biopsy will be performed of the opposite side of the lower abdomen than where the first biopsy was taken. In addition, monthly liver function studies will be performed to detect possible elevations of serum transaminase levels above the normal range during flutamide vs. placebo therapy.

Menstrual records and urinary pregnanediol glucuronide (UPDG): Ovulatory frequency will be determined by having subjects keep a daily menstrual record and collect weekly first morning urine samples for UPDG and creatinine assay. Urine samples will be stored for later analysis. Urine samples will be analyzed at the University of Wisconsin-Wisconsin National Primate Research Center for the urinary metabolite of progesterone (urinary pregnanediol glucuronide [UDPG]) and creatinine testing.

Six months following the completion of protocol procedures, participants who received flutamide/placebo will be contacted by phone to check on the status of their health. Subjects will be asked if they have experienced any health problems or have become pregnant since they completed the study procedures.

Daily diaries will include self reporting on taking pills, menstrual flow, symptoms, concomitant medications, exercise patterns, and diet habits.

Quality of life assessments and ovarian size measurements will be conducted at baseline, and at the end of 3 and 6 months of treatment. The PHQ, Beck's Anxiety, Beck's Depression questionnaires will be completed at baseline. The Beck's Depression and Beck's Anxiety will be completed at 3 and 6 month visits. Scoring of the Quality of Life surveys (Beck's anxiety and Beck's depression questionnaires) will be at the time the subject is present for their study visit. If any areas of concern are identified, they will be addressed with the subject before they leave and the appropriate referrals

Revised 3-7-18 UCLA IRB #12-001780 Page 8 of 27

will be made.

In order to conduct quality control testing on the urine samples, we are requesting approval to utilize urine specimens from IRB #11-001454, "A Study to Collect Specimens and Medical Information for Use in Research" - PI - [name] and UCLA IRB #13-000430 "A study to learn more about the optimal conditions for storing and shipping urine samples for research purposes" - PI - [name]. We will also utilize blood and tissue samples from participants in IRB #11-001454 in order to conduct further laboratory tests including immunohistological assessments which will allow us to integrate adipose/hormonal data to more fully investigate the pathophysiology processes of diseases under study. Specimens may be analyzed in [name] lab at UCLA and/or shipped for analysis to [name].; Wisconsin National Primate Research Center, [name].

Participants will be given the opportunity to sign a minimal risk consent form if they wish to communicate by e-mail during their participation in this study.

In December, 2013 an amendment was submitted for this study requesting a change from using the OGTT test to an FSIGT test. Subjects in the control arm who have already undergone an OGTT test and do not wish to undergo an FSIGT test will not be affected and the data from their OGTT test will be used. Subjects in the PCOS arm who have undergone an OGTT test at baseline may choose to repeat a baseline FSIGT test and have an FSIGT test at the end of study. If they do not wish to have an FSIGT test, an OGTT test will be performed at the end of study.

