Per amendment #42, epigenetic studies (RNA sequencing, DNA Methylation, and Assay for Transposase Accessible Chromatin Sequencing) on existing fat cell samples will be conducted at UCLA.

INCLUSION CRITERIA

Caucasian and Non-Hispanic women between the ages of 18 to 35 years.

Groups will be: 12 lean controls (Aim 1); 36 age- and BMI-matched PCOS women randomized to flutamide vs. placebo for 6 months (Aims 1 and 2).

i) Lean patients with PCOS: 36 subjects with PCOS (defined by 1990 NIH criteria [all Aims]), BMI 18.5-25 kg/m2. This BMI range is defined as normal and has been chosen to examine underlying mechanisms of PCOS-related androgen excess in the genesis of adipogenic and ovarian dysfunction, independent of obesity. Excessive course hair on upper lip, chin, chest, upper back, lower back, upper abdomen, lower abdomen, arm and/or thigh.

ii) Lean control women: 12 healthy subjects, BMI 18.5-25 kg/m2. Controls will have regular menstrual cycles, and no evidence of hirsutism, acne, alopecia, polycystic ovaries, and/or endocrine dysfunction. This BMI range has been chosen to match that of the PCOS group.

Up to 70 lean PCOS patients and 20 lean controls will be recruited, for a total of 90 study participants over a 5-year interval, accounting for a 20% rate of patient drop-out or insufficient adipose procurement. Participants must be fluent in English.

EXCLUSION CRITERIA

Exclusion criteria for study participation are: present or past history of smoking within past 1 year, cancer, alcohol abuse within past 5 years, drug addiction within past 5 years, severe depression within past 5 years, or post traumatic stress disorder within

Revised 3-7-18 UCLA IRB #12-001780 Page 10 of 27

past 5 years; diabetes; uncontrolled hypertension (≥ 165/100); clinically significant hepatic or renal disease, or other major medical illness; recent (within 3 months) use of androgens, anabolic steroids or hormonal agents (including birth control pills or insulin sensitizers), Mirena IUD, or Plan B contraception. These exclusion criteria are chosen to avoid effects from medical conditions, environmental factors or exogenous agents. Women taking the drug warfarin, beta blockers, CYP active medications, or herbs will be excluded.

Since this study involves MRI testing, women with pacemakers, metal implants, or claustrophobia will be excluded.

The screener will assess the participants response to establish if depression or drug use exclude participation in this study.

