• The first blood draw will be sent to the laboratory for an immediate test of their progesterone level which indicates whether or not they are ovulating. If the progesterone test indicates that they are ovulating, the FSH test will not be able to be performed that day and will need to be rescheduled. If the test cannot be performed, they will be paid \$10 for this visit and another appointment will be scheduled.

• It will be necessary for them to stay at UCLA Medical Center in the Clinical Translational Research Center, which is located in the Center for Health Sciences building for approximately 26 hours in order to complete this test. Food will be provided to them during the testing.

• Approximately 1-2 tablespoons (21 mL) of blood will be drawn from their vein.

If subjects have PCOS, an additional 4 mL (approximately 1 teaspoon) of blood will be drawn for a complete blood count and comprehensive metabolic panel in order to assure that there are no abnormalities in these blood values before they begin taking flutamide or placebo.

Since some of the blood tests to confirm hormonal levels are timed around different phases of the menstrual cycle and menstrual cycles vary, it is possible some of the blood tests described above will need to be repeated. The Frequently Sampled

Intravenous Glucose Tolerance Test and the Follicle Stimulating Hormone Test will only be performed as described above.

Subjects will be paid \$280 once they have completed the FSIGT, DXA, MRI, Fat Removal, and FSH stimulation visits. If they report to UCLA for a study visit and their blood tests indicate that they are not in the desired part of their menstrual cycle for a particular test, they will be compensated an additional \$10 and the visit will be rescheduled. Participants will be asked to complete a form so that a check can be mailed to them within 2 months.

Women who do not have PCOS will conclude their participation in this study at this point. No further procedures for this study will be conducted.

Women with PCOS will continue participation as described below.

Women with PCOS will be asked to do the following:

• Take one pill (either placebo or flutamide) each morning before breakfast for 6 complete 28 day cycles. The drug flutamide has not been approved by the FDA for use in women or for the treatment of PCOS.

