We will use one-way factorial analysis of variance (ANOVA) methods to compare continuous outcomes including hormone levels; adipocyte size, lipid content and glycerol release; numbers of ASCs and preadipocytes; mRNA levels. If data are not normally distributed on any scale, we will carry out nonparametric ANOVA.

Our previous comparison of cFOS gene expression in PCOS women vs. controls showed an increase in Δ Ct (6.0 ± 1.4). Based on this, we hypothesize that the mean difference between controls and IR PCOS is 1.7 SD units. Assuming this, a sample size of 8/group (IR vs. non-IR PCOS) provides over 80% power using the usual two-sided p < 0.05.

We also will compare all outcomes before vs. after 6 months of placebo or flutamide treatment controlling for IR status, using either the parametric paired t test or non-parametric Wilcoxon signed rank test. Insulin action and sensitivity will be assessed by calculating a Matsuda Index from blood glucose and insulin levels during the oral glucose tolerance test. Ovarian estradiol sensitivity to FSH will be calculated from the 24-hr area-under-the-curve (AUC) serum estradiol response to FSH infusion.

Based on our in vitro data, we observed a mean 0.17 log scale change in Δ Ct PPAR γ (SD=0.26 log units) after treatment with T + Flutamide vs. T alone. A sample size of 14 (7 non-IR, 7 IR) provides more than 80% power for the IR adjusted mean change.

REFERENCES

3. 2004. Revised 2003 consensus on diagnostic criteria and long-term health risks related to polycystic ovary syndrome. Fertil Steril 81(1):19-25.

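### Aim 2 hypothesises that flutamide normalizes adipose storage, but no stated analysis shows whether treated women reach the control level

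*Combined protocol and SAP*

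**What the plan says.** **Aims and Objectives.** Aim 1 compares lean PCOS women with age- and BMI-matched controls and hypothesises that their subcutaneous abdominal storage is constrained. Aim 2 then states: "Hypothesis: SC abdominal adipose storage is normalized in lean PCOS women receiving flutamide". No storage measure, normal range or margin defines the word.

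**Statistical Considerations.** Two analyses are named.
- A between-group one: "We will use one-way factorial analysis of variance (ANOVA) methods to compare continuous outcomes including hormone levels". The groups and the time point are not given.
- One for the treatment period: "We also will compare all outcomes before vs. after 6 months of placebo or flutamide treatment controlling for IR status", by paired t test or Wilcoxon signed rank test. The Aim 2 power statement also concerns a mean change.

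**Background, on the effect of flutamide.** The protocol intends a systematic comparison in "lean PCOS women randomized to 6-month low-dose flutamide vs. placebo to determine how differences in key variables affect" ovarian function. No test is attached, and controls are not part of it.

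**Controls.** The Inclusion Criteria list the groups as "12 lean controls (Aim 1); 36 age- and BMI-matched PCOS women randomized to flutamide vs. placebo for 6 months", so controls are assigned to Aim 1 only. After the baseline tests, Procedures says: "Women who do not have PCOS will conclude their participation in this study at this point".

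**Data available.** Controls and PCOS women have the same procedures at the start. For PCOS women, Research Design and Methods (Aim 2) adds: "All adipogenic studies performed at study initiation will be repeated at the end of the 6 - 28 day cycles" of treatment.

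**The concern.** Normalization is a statement about where treated women end up relative to women without PCOS. A paired test asks only whether they moved. A difference from placebo asks whether the drug moved them. Either result is compatible with stopping well short of the control level or with overshooting it.

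At stake is whether the trial can answer its own Aim 2 hypothesis. As written, the analysis can neither confirm nor refute it. If the paired result is significant, the plan contains nothing to stop that result being described in the hypothesis's own word. The obvious informal substitute, that treated women no longer differ significantly from controls, is not proposed in the plan. It would be weak evidence at this sample size.

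**Working it through.** **Inputs from the protocol.** 36 PCOS women and 12 controls expected to complete; control versus insulin-resistant PCOS gap 1.7 SD; Aim 2 change 0.17 with SD 0.26, n = 14; two-sided 0.05, stated for the 8-per-group figure.

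**Assumptions.** Allocation 1:1, so 18 flutamide completers (the ratio is not stated); equal SDs; within-woman correlation ρ from 0.3 to 0.7. The 1.7 SD gap concerns one gene in insulin-resistant women and serves only as illustration.

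**1. The plan's own power figures.**
- 8 per group at 1.7 SD: two-sample t power is 88.5%, so the claim that this size "provides over 80% power using the usual two-sided p < 0.05" reproduces.
- n = 14, d = 0.17/0.26 = 0.654: paired t power is 61.9% two-sided, so the stated figure of more than 80% does not reproduce at that level. It would need a residual SD of about 0.21 or less, which is not stated. This is a separate matter. For the present point, what counts is that the figure is for a change, with no control value in it.

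**2. Can the paired test succeed while normalization fails?** Let flutamide close half the gap: change 0.85 SD, remaining deficit 1.7 − 0.85 = 0.85 SD. SD of the change = √(2(1 − ρ)); noncentrality = 0.85/√(2(1 − ρ)) × √18; critical t on 17 df = 2.110.

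| ρ | SD of change | Noncentrality | Power, n = 18 | Power, n = 14 |
|---|---|---|---|---|
| 0.3 | 1.183 | 3.05 | 82% | 70% |
| 0.5 | 1.000 | 3.61 | 92% | 84% |
| 0.7 | 0.775 | 4.66 | 99% | 97% |

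The result depends on the size of the gap. If the gap were 1.0 SD and half closed (change 0.5 SD, 0.5 SD remaining), power with 18 women would be 39%, 52% and 73%.

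**3. Precision of flutamide minus control at end of treatment.** SE = √(1/18 + 1/12) = 0.3727 SD. The 95% half-width is 2.048 × 0.3727 = 0.76 SD (0.81 SD with 14 versus 12).

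**4. What a non-significant difference from controls would mean.** Two-sample t test, 18 versus 12, noncentrality = remaining gap/0.3727:

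| Remaining gap (SD) | Power | Chance of non-significance |
|---|---|---|
| 0.50 | 25% | 75% |
| 0.75 | 49% | 51% |
| 0.85 | 60% | 40% |
| 1.00 | 74% | 26% |

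Power of 80% needs a gap of about 1.08 SD.

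**5. Would a formal equivalence test work?** Two one-sided tests at 0.05, true difference zero, 18 versus 12, by simulation: power 0.4% at a margin of 0.5 SD, 26% at 0.75, 67% at 1.0, 90% at 1.25 and 98% at 1.5.

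**The case against.** The strongest reply is that *normalized* is loose, directional wording. The Aim 2 heading speaks of examining an effect, its bullets of determining changes, and the Background of improving adipogenic function. On that reading the working question is change under treatment. This has force, but it argues for rewording the hypothesis, not for leaving it.

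Several stronger readings are tempting, and the documents do not support them.
- A reader might infer that the plan uses controls solely in a baseline ANOVA. The ANOVA sentence names neither groups nor time point, so it could be stretched to post-treatment values. The plan does not say so, and an ANOVA tests for a difference, not for arrival at the control level.
- A reader might infer that no comparison with placebo is planned. The Background states that intention; what is missing is a test.
- A reader might infer that a small improvement would be declared normalized. With 18 women, a change of 0.3 SD (in SDs of the change) has only about 22% power, and the documents nowhere say how a partial improvement will be described.

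It is also fair that the added comparison is weak. It is non-randomised, and controls are assessed once, so drift over six months is uncontrolled on their side. The protocol has controls studied in the follicular phase and PCOS women during amenorrhea, and the second biopsy is on the opposite side. The documents offer no basis for a margin. If the whole 1.7 SD gap remained, the 18 versus 12 comparison would detect it about 99% of the time, so low power concerns partial deficits. These limits are why the comparison should be supportive and reported as an estimate.

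**Conclusion.** The point stands as a gap in the analysis plan, not in data collection. No analysis stated in the text available compares post-flutamide values with controls; a part of the methods was not in that text, but the statistical section was.

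A significant before-after change would be likely (82% to 99%) with half of a 1.7 SD gap still open. This assumes 18 flutamide completers, equal SDs and ρ of 0.3 to 0.7, with a gap borrowed from one gene in insulin-resistant women. A smaller gap lowers those probabilities. The underlying argument needs no figure: none of the stated comparisons measures distance from the control level.

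A reader might go further and conclude that a formal equivalence test is required. At 18 versus 12 its power is low for margins under about 1 SD, even if normalization were complete. The conclusion is therefore narrower: estimate the remaining difference and keep the claim within what that estimate shows. It should be corrected because it concerns the Aim 2 headline hypothesis and the change is cheap.

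**What to change.** In Statistical Considerations:
1. State a test for the randomised flutamide versus placebo comparison as the main Aim 2 analysis.
2. Beside it, add a supportive comparison of end-of-treatment flutamide values with the controls' single assessment. Limit it to named adipose storage outcomes, adjust for age and BMI, and report the remaining difference with its 95% CI.
3. State that neither a significant before-after change nor a non-significant difference from controls will be read as normalization.
4. Name the groups and the time point of the ANOVA.

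In Aims and Objectives, reword the Aim 2 hypothesis to improvement toward control values, unless a margin is justified in advance. An equivalence test and the share of the gap closed are optional; the latter is a ratio whose denominator rests on 12 controls and is unstable if the gap is small.

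**Cost.** No new visits, samples or participants: one added analysis on data already collected, and a wording change. The report must name the limits of the comparison (non-randomised, controls measured once, different cycle states), and the claim will probably weaken.
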